13.3. Clinical Study Report

An integrated CSR will be prepared in accordance with the standards of the ICH guideline for structure and content of clinical study reports (ICH E3). Copies of the CSR will be provided to the IEC/IRB and the national regulatory authority in accordance with regulatory requirements and PAREXEL SOPs. In the event of premature termination of the study or other conditions specified in ICH E3, an abbreviated CSR may be prepared.

15. APPENDICES

15.1. Additional Safety Information

FURTHER GUIDANCE ON THE DEFINITION OF A SERIOUS ADVERSE EVENT

Life-threatening

‘Life-threatening’ means that the subject was at immediate risk of death from the AE as it occurred or it is suspected that use or continued use of the product would result in the subject’s death. ‘Life-threatening’ does not mean that had an AE occurred in a more severe form it might have caused death (e.g., hepatitis that resolved without hepatic failure).

Hospitalization

Outpatient treatment in an emergency room is not in itself a SAE, although the reasons for it may be (e.g., bronchospasm, laryngeal edema). Hospital admissions and/or surgical operations planned before or during a study are not considered AEs if the illness or disease existed before the subject was enrolled in the study, provided that it did not deteriorate in an unexpected way during the study.

Important medical event or medical intervention

Medical and scientific judgment should be exercised in deciding whether a case is serious in situations where important medical events may not be immediately life-threatening or result in death, hospitalization, disability or incapacity but may jeopardize the subject or may require medical intervention to prevent 1 or more outcomes listed in the definition of serious. These should usually be considered as serious.

Simply stopping the suspect drug does not mean that it is an important medical event; medical judgment must be used.

Examples of such events are:

- Angioedema not severe enough to require intubation but requiring IV hydrocortisone treatment.
- Hepatotoxicity caused by paracetamol/acetaminophen overdose requiring treatment with N-acetyl cysteine.
- Intensive treatment in an emergency room or at home for allergic bronchospasm.
- Blood dyscrasias (e.g., neutropenia or anemia requiring blood transfusion) or convulsions that do not result in hospitalization.

- Development of drug dependency or drug abuse.

A GUIDE TO INTERPRETING THE CAUSALITY QUESTION

The following factors should be considered when deciding if there is a “reasonable possibility” that an AE may have been caused by the investigational medicinal product (IMP).

- **Time Course / Exposure to suspect drug**

Has the subject actually received the suspect drug? Did the AE occur in a reasonable temporal relationship to the administration of the suspect drug?

- **Consistency with known drug profile**

Was the AE consistent with the previous knowledge of the suspect drug (pharmacology and toxicology) or drugs of the same pharmacological class? OR, could the AE be anticipated from its pharmacological properties?

- **Dechallenge experience**

Did the AE resolve or improve on stopping or reducing the dose of the suspect drug?

- **No alternative cause**

The AE cannot be reasonably explained by other etiology such as the underlying disease, other drugs, other host or environmental factors.

- **Rechallenge experience**

Did the AE reoccur if the suspected drug was reintroduced after having been stopped?

Note: AstraZeneca would not normally recommend or support a rechallenge.

- **Laboratory tests**

A specific laboratory investigation (if performed) has confirmed the relationship?

A “reasonable possibility” could be considered to exist for an AE where 1 or more of these factors exist.

In contrast, there would not be a “reasonable possibility” of causality if none of the above criteria apply or where there is evidence of exposure and a reasonable time course but any dechallenge (if performed) is negative or ambiguous or there is another more likely cause of the AE.

In difficult cases, other factors could be considered such as:

- Is this a recognized feature of overdose of the drug?
- Is there a known mechanism?

Ambiguous cases should be considered as being a “reasonable possibility” of a causal relationship, unless further evidence becomes available to refute this. Causal relationship in cases where the disease under study has deteriorated due to lack of effect should be classified as no reasonable possibility.

15.2. International Airline Transportation Association (IATA) 6.2 Guidance Document

LABELLING AND SHIPMENT OF BIOHAZARD SAMPLES

International Airline Transportation Association (IATA) classifies bio hazardous agents into 3 categories (http://www.iata.org/whatwedo/cargo/dangerous_goods/infectious_substances.htm). For transport purposes the classification of infectious substances according to risk groups was removed from the Dangerous Goods Regulations (DGR) in the 46th edition (2005). Infectious substances are now classified either as Category A, Category B or Exempt. There is no direct relationship between Risk Groups and Categories A and B.

CATEGORY A

Category A Infectious Substances are infectious substances in a form that, when exposure to it occurs, is capable of causing permanent disability, life-threatening or fatal disease in otherwise healthy humans or animals. Category A pathogens are for example, Ebola and Lassa Fever viruses. Category A pathogens:

Are to be packed and shipped in accordance with IATA Instruction 602.

CATEGORY B

Category B Infectious Substances are infectious substances that do not meet the criteria for inclusion in Category A. Category B pathogens are for example, hepatitis A, B, C, D and E viruses, and HIV types 1 and 2. They are assigned the following UN number and proper shipping name:

- UN 3373 – Biological Substance, Category B

Category B pathogens:

- Are to be packed in accordance with UN3373 and IATA Instruction 650.

EXEMPT

Exempt refers to all other materials with minimal risk of containing pathogens.

- Clinical trial samples will fall into Category B or Exempt under IATA regulations.
- Clinical trial samples will routinely be packed and transported at ambient temperature in IATA 650 compliant packaging.

(http://www.iata.org/whatwedo/cargo/dangerous_goods/infectious_substances.htm)

- **Biological samples transported in dry ice require additional dangerous goods specification for the dry-ice content.**
- IATA compliant courier and packaging materials should be used for packing and transportation. Packing should be done by an IATA certified person, as applicable.
- Samples routinely transported by road or rail are subject to local regulations which require that they are also packed and transported in a safe and appropriate way to contain any risk of infection or contamination by using approved couriers and packaging / containment materials at all times.

The IATA 650 biological sample containment standards are encouraged wherever possible when road or rail transport is used.

15.3. Actions Required in Cases of Combined Increase of Aminotransferase and Total Bilirubin - Hy's Law

1. INTRODUCTION

During the course of the study, the investigator will remain vigilant for increases in liver clinical chemistry. The investigator is responsible for determining whether a subject/patient meets potential Hy's Law (PHL) criteria at any point during the study.

The investigator participates, together with AstraZeneca clinical project representatives, in review and assessment of cases meeting PHL criteria to agree whether Hy's Law (HL) criteria are met. The HL criteria are met if there is no alternative explanation for the elevations in liver clinical chemistry other than Drug Induced Liver Injury (DILI) caused by the investigational medicinal product (IMP).

The investigator is responsible for recording data pertaining to PHL/HL cases and for reporting AEs and SAEs according to the outcome of the review and assessment in line with standard safety reporting processes.

2. DEFINITIONS

Potential Hy's Law (PHL)

- Aspartate aminotransferase (AST) or alanine aminotransferase (ALT) $\geq 3x$ upper limit of normal (ULN) **and** total bilirubin (TBL) $\geq 2x$ ULN at any point during the study irrespective of an increase in alkaline phosphatase (ALP)
- The elevations do not have to occur at the same time or within a specified time frame

Hy's Law (HL)

- AST or ALT $\geq 3x$ ULN **and** TBL $\geq 2x$ ULN, where no other reason, other than the IMP, can be found to explain the combination of increases, e.g., elevated ALP indicating cholestasis, viral hepatitis, another drug
- The elevations do not have to occur at the same time or within a specified time frame

3. IDENTIFICATION OF POTENTIAL HY'S LAW CASES

In order to identify cases of PHL it is important to perform a comprehensive review of laboratory data for any subject/patient who meets any of the following identification criteria in isolation or in combination:

- ALT $\geq 3x$ ULN
- AST $\geq 3x$ ULN

- TBL \geq 2x ULN

The investigator will review without delay each new laboratory report and if the identification criteria are met will:

- Notify the AstraZeneca representative
- Determine whether the subject/patient meets PHL criteria (see Section 2 of this Appendix for definition) by reviewing laboratory reports from all previous visits
- Promptly enter the laboratory data into the laboratory case report form (CRF)

4. FOLLOW-UP

4.1 Potential Hy's Law Criteria not met

If the subject/patient does not meet PHL criteria the investigator will:

- Inform the AstraZeneca representative that the subject/patient has not met PHL criteria
- Perform follow-up on subsequent laboratory results according to the guidance provided in the clinical study protocol

4.2 Potential Hy's Law Criteria met

If the subject/patient does meet PHL criteria the investigator will:

- Notify the AstraZeneca representative who will then inform the central study team.

The study physician contacts the investigator, to provide guidance, discuss and agree an approach for the study subjects'/patients' follow-up and the continuous review of data.

Subsequent to this contact the investigator will:

- Monitor the subject/patient until liver clinical chemistry variables and appropriate clinical symptoms and signs return to normal or baseline levels, or as long as medically indicated.
- Investigate the etiology of the event and perform diagnostic investigations as discussed with the study physician.
- Complete the 3 Liver CRF Modules as information becomes available.

If at any time (in consultation with the study physician) the PHL case meets serious criteria, report it as an SAE using standard reporting procedures.

5. REVIEW AND ASSESSMENT OF POTENTIAL HY'S LAW CASES

The instructions in this section should be followed for all cases where PHL criteria were met.

No later than 3 weeks after the clinical chemistry abnormality was initially detected, the study physician contacts the investigator in order to review available data and agree on whether there is an alternative explanation for meeting PHL criteria other than DILI caused by the IMP. The AstraZeneca Medical Science Director and Global Safety Physician will also be involved in this review together with other subject matter experts as appropriate.

According to the outcome of the review and assessment, the investigator will follow the instructions below.

If there is an agreed alternative explanation for the ALT or AST and TBL elevations, a determination of whether the alternative explanation is an AE will be made and subsequently whether the AE meets the criteria for an SAE:

- If the alternative explanation is **not** an AE, record the alternative explanation on the appropriate CRF
- If the alternative explanation is an AE/SAE, record the AE /SAE in the CRF accordingly and follow the AstraZeneca standard processes

If it is agreed that there is **no** explanation that would clarify the ALT or AST and TBL elevations other than IMP causality:

- Report an SAE (report term ‘Hy’s Law’) according to AstraZeneca standard processes.
 - The ‘Medically Important’ serious criterion should be used if no other serious criteria apply
 - As there is no alternative explanation for the HL case, a causality assessment of ‘related’ should be assigned

If, there is an unavoidable delay, of over 3 weeks, in obtaining the information necessary to assess whether or not the case meets the criteria for HL, then it is assumed that there is no alternative explanation until such time as an informed decision can be made:

- Report an SAE (report term ‘Potential Hy’s Law’) applying serious criteria and causality assessment as per above
- Continue follow-up and review according to agreed plan. Once the necessary supplementary information is obtained, repeat the review and assessment to determine whether HL criteria are met. Update the SAE report according to the outcome of the review [4].

15.4. Guidance for abnormal Pap smear results

Pap Smear Result	Abbreviation	Also Known As	Suggested Action
Atypical squamous cells–undetermined significance	ASC–US	—	Permitted to enter study
Atypical squamous cells–cannot exclude HSIL	ASC–H	—	Permitted to enter study
Atypical glandular cells	AGC	—	Permitted to enter study
Low-grade squamous intraepithelial lesion	LSIL	Mild dysplasia Cervical intraepithelial neoplasia–1 (CIN–1)	Permitted to enter study
High-grade squamous intraepithelial lesion	HSIL	Moderate dysplasia CIN-2 / CIN II	Permitted to enter study
High-grade squamous intraepithelial lesion	HSIL	CIN–3 / CIN III Carcinoma in situ (CIS)	Exclude/discontinue subject
Endocervical adenocarcinoma in situ	AIS	—	Exclude/discontinue subject

15.5. Anaphylaxis

In adults, anaphylaxis is highly likely when any 1 of the following 3 criteria is fulfilled:

1. Acute onset of an illness (minutes to several hours) with involvement of the skin, mucosal tissue, or both (e.g., generalized hives, pruritus or flushing, swollen lips, tongue and/or uvula)

AND AT LEAST ONE OF THE FOLLOWING:

- Respiratory compromise (e.g., dyspnea, wheeze-bronchospasm, stridor, reduced peak expiratory flow, hypoxemia)
 - Reduced BP (see number 3 below for definition) or associated symptoms of end-organ dysfunction (e.g., hypotonia [collapse], syncope, incontinence)
2. Two or more of the following that occur rapidly after exposure to a likely allergen for that subject (minutes to several hours):
 - Involvement of the skin-mucosal tissue (e.g., generalized hives, itch, flush, swollen lips, tongue and/or uvula)
 - Respiratory compromise (e.g., dyspnea, wheeze-bronchospasm, stridor, reduced peak expiratory flow, hypoxemia)
 - Reduced BP (see number 3 below for definition) or associated symptoms (e.g., hypotonia [collapse], syncope, incontinence)
 - Persistent gastrointestinal symptoms (e.g., crampy abdominal pain, vomiting)
 3. Reduced BP after exposure to known allergen for that subject (minutes to several hours); for adults a systolic BP of less than 90 mm Hg or greater than 30% decrease from that person's baseline BP (taken at or immediately prior to start of the infusion), whichever BP is lower.

The following definitions are provided for the purposes of this study:

Hypersensitivity reaction: an acute onset of an illness with involvement of the skin, mucosal tissue, or both during infusion of investigational product (but does not meet the definition of anaphylaxis described above).

Infusion-related reaction: any other reaction occurring during infusion of investigational product or felt to be temporally related to the infusion within 24 hours of investigational product administration.

To assist with the mitigation of these AEs, see [Table 4](#), which categorizes reactions by severity of symptoms, proposes severity-specific treatment and offers guidance on management of investigational product. Final treatment is at the discretion of the Investigator and should reflect local SOC.

Table 4 An Approach to Management of Anaphylactic, Hypersensitivity, and Infusion-Related Reactions

Severity of symptoms	Treatment	Investigational product

Mild reactions (infusion and hypersensitivity) Mild infusion-related reactions such as headache, nausea, non-pruritic rash, or mild hypersensitivity reactions including localized cutaneous reactions such as mild pruritus, flushing, rash, dizziness, headache, ≤ 20 mmHg change in systolic BP from pre-infusion measurement
	
Evaluate subject, including close monitoring of vital signs At the discretion of the Investigator, treat subject, for example, with:
 
 - Normal saline (~500 to 1000 mL/hour IV) and/or - Diphenhydramine 50 mg IV or equivalent and/or - Acetaminophen 500 to 650 mg or equivalent dose of paracetamol and/or - Topical antihistamines and/or low-potency topical corticosteroid preparations and/or - Anti-nausea medication, as needed 	
Stop investigational product infusion immediately Option 1: do not resume investigational product infusion; OR at the discretion of the Investigator, resume current investigational product infusion under observation and complete investigational product infusion at no more than half the planned infusion rate Option 2: discontinue any further administration of investigational product; OR at the discretion of the Investigator, continue future investigational product administrations and consider slowing infusion rate and pretreating subject 1.5 to 0.5 hours prior to investigational product administration, for example with:
 
 - Diphenhydramine 50 mg IV or equivalent - Acetaminophen 500 to 650 mg or equivalent dose of paracetamol

Moderate reactions (infusion) Infusion-related reaction such as those listed above under mild reactions but excluding moderate hypersensitivity reactions (see below)
	
Evaluate subject, including close monitoring of vital signs Treat subject, for example, with:
 
 - Normal saline (~500 to 1000 mL/hour IV) and/or - Diphenhydramine 50 mg IV or equivalent and/or - Acetaminophen 500 to 650 mg or equivalent dose of paracetamol and/or - Anti-nausea and/or antiemetic intramuscular, as needed 	
Stop investigational product infusion immediately Option 1: do not resume investigational product infusion; OR based on risk/benefit evaluation, at the discretion of the Investigator, resume current investigational product infusion under observation and at no more than half the planned infusion rate after treatment of current signs and symptoms as suggested (e.g., normal saline and/or and/or topical antihistamines)

Severity of symptoms	Treatment	Investigational product
		
Additional Options for Future Administration of investigational product
 
Discontinue any further administrations of investigational product; OR
 
Further investigational product infusions, at the discretion of the Investigator, continue investigational product administration and consider slowing infusion rate and pretreating subject 0.5 to 1.5 hours prior to investigational product administration, for example with:
 
- Diphenhydramine 50 mg IV or equivalent- Acetaminophen 500 to 650 mg or equivalent dose of paracetamol- Anti-nausea and/or antiemetic by mouth 
Prior to next administration of investigational product administration, consider initiating at a slower infusion rate and pretreating subject 0.5 to 1.5 hours prior to next administration of investigational product, for example, with
 
- Diphenhydramine 50 mg IV or equivalent- Acetaminophen 500 to 650 mg or equivalent dose of paracetamol 
If moderate event recurs in the same subject, discontinue further investigational product administration

Severity of symptoms	Treatment	Investigational product

Moderate hypersensitivity reactions Infusion related reactions which may include generalized rash or urticaria, palpitations, chest discomfort, shortness of breath, hypo- or hypertension with >20 mmHg change in systolic BP from pre-infusion measurement
	
Evaluate subject, including close monitoring of vital signs Treat subject, for example, with:
 
 - Normal saline (~500 to 1000 mL/hour IV) and/or - Diphenhydramine 50 mg IV or equivalent and/or - Acetaminophen 500 to 650 mg or equivalent dose of paracetamol and/or - IV corticosteroids, such as hydrocortisone 100 mg or methylprednisolone 20 to 40 mg 	
Stop investigational product infusion immediately DO NOT resume current infusion Discontinue any further administrations of investigational product Consider need for additional oral antihistamine administration or oral corticosteroid administration to prevent reoccurrence of symptoms over subsequent 2 to 3 days


Severe Above plus fever with rigors, hypo- or hypertension with ≥40 mmHg change in systolic BP, signs of end organ dysfunction (e.g., symptomatic hypotension such as hypotonia, syncope, incontinence, seizure) from pre-infusion measurement, or wheezing, angioedema, or stridor OR Life-threatening Defined as a reaction that is life-threatening and requires pressor and/or ventilator support or shock associated with acidemia and impairing vital organ function due to tissue hypoperfusion
	
Evaluate subject, including close monitoring of vital signs Maintain airway, oxygen if available Treat subject immediately, for example with:
 
 - Normal saline (~500 to 1000 mL/hour IV) - Epinephrine for bronchospasm, hypotension unresponsive to IV fluids, or angioedema. Dose and route as per local SOC, example, epinephrine 1:1000, 0.5 to 1.0 mL administered SC for mild cases and intramuscular for more severe cases - IV corticosteroids, such as hydrocortisone 100 mg or methylprednisolone 20 to 40 mg - Diphenhydramine 50 mg IV or equivalent - Acetaminophen 500 to 650 mg or equivalent dose of paracetamol 
Call emergency medical transport for transport to emergency hospital based on judgment of the Investigator Grade 3 wheezing, hypotension or angioedema is unresponsive to single dose of epinephrine Grade 4 event At the discretion of the Investigator
	
Stop investigational product infusion immediately Do not resume current infusion Permanently discontinue investigational product administration Consider need for additional oral antihistamine administration or oral corticosteroid administration to prevent reoccurrence of symptoms over subsequent 2 to 3 days

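### Appendix 15.5 classes an acute reaction with generalized urticaria and shortness of breath as anaphylaxis, but Table 4 lists both features under moderate hypersensitivity and has no anaphylaxis row; the blood pressure limit in criterion 3 can also be read two ways

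*Protocol*

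**What the plan says.** Section 12.1.3.3 points to Appendix 15.5 for the study's definition of anaphylaxis. The appendix opens: "In adults, anaphylaxis is highly likely when any 1 of the following 3 criteria is fulfilled". Criterion 1 has a skin limb, "Acute onset of an illness (minutes to several hours) with involvement of the skin, mucosal tissue, or both (e.g., generalized hives", and needs at least one further item. One such item is "Respiratory compromise (e.g., dyspnea, wheeze-bronchospasm, stridor, reduced peak expiratory flow, hypoxemia".

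The appendix then defines a hypersensitivity reaction as an acute illness of skin or mucosa "during infusion of investigational product (but does not meet the definition of anaphylaxis described above". By definition, the two classes do not overlap.

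Table 4 covers the management of anaphylactic, hypersensitivity and infusion-related reactions, according to its title. Its row for moderate hypersensitivity reads: "Infusion related reactions which may include generalized rash or urticaria, palpitations, chest discomfort, shortness of breath", followed by a systolic change of more than 20 mmHg. The severe row adds further signs: fever with rigors, a systolic change of at least 40 mmHg, end-organ dysfunction, wheezing, angioedema or stridor, or a life-threatening reaction. No row carries the label anaphylaxis.

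Criterion 3 gives two adult limits for reduced blood pressure, a systolic value under 90 mmHg or a fall of more than 30% from baseline. It closes with "whichever BP is lower".

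Anaphylaxis is on the AESI list in Section 12.1.3; hypersensitivity reaction is not. Section 12.3 requires AESIs to be reported within 24 hours whether serious or not, and Section 11.11.1 gives them a separate tabulation.

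**The concern.** The appendix contains both the definition that decides whether an event is anaphylaxis and the table that staff would consult during a reaction. If the table describes as moderate hypersensitivity a combination of signs that the definition calls anaphylaxis, one event can receive either label depending on which page the assessor follows. An assessor who applies the definition strictly then finds no row in Table 4 for the event.

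The label matters for the analysis because safety and tolerability is a primary objective (Section 6.1) and AESIs are tabulated on their own. It matters for conduct because only one of the two labels triggers 24-hour AESI reporting when the event is not otherwise serious. The wording of criterion 3 adds a second source of inconsistent classification. Criteria 1 and 2 both refer to criterion 3 for their meaning of reduced blood pressure.

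**Working it through.** The protocol gives no figure to reproduce here. The first check is logical and the second is arithmetic.

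**Classification.** Take an acute reaction during infusion with generalized urticaria and shortness of breath and no other sign.

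| Text in Appendix 15.5 | Requirement | Met? |
|---|---|---|
| Criterion 1 | acute skin involvement plus one item, e.g. dyspnea | yes |
| Criterion 2 | two or more listed items soon after a likely allergen | yes, if the product counts as a likely allergen |
| Hypersensitivity definition | must not meet the anaphylaxis definition | no, excluded |
| Table 4, moderate hypersensitivity | may include generalized urticaria and shortness of breath | yes |
| Table 4, severe | further signs as listed above | no |
| Table 4, anaphylaxis | no such row | – |

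The definition makes the event anaphylaxis and bars it from the hypersensitivity class. The only hypersensitivity row that describes it is therefore closed to it, the severe row is not reached, and no other row is assigned to it.

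**Reporting.** Labelled anaphylaxis, the event is an AESI, due within 24 hours and counted in the AESI table. Labelled hypersensitivity and not serious, it is an ordinary adverse event. Section 8.6 plans 6 active subjects per cohort, so one relabelled event moves an arm's AESI proportion by 1/6 = 16.7 percentage points.

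**Criterion 3.** Let B be the baseline systolic pressure. A fall of more than 30% means a value below 0.7 × B.

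- 'Or' reading: reduced if the value is below 90 or below 0.7 × B, so the limit is max(90, 0.7 × B).
- 'Lower' reading: the limit is min(90, 0.7 × B).
- The two limits coincide only at B = 90/0.7 = 128.6 mmHg.

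| B | 0.7 × B | Value reached | Fall | 'Or' reading | 'Lower' reading |
|---|---|---|---|---|---|
| 110 | 77 | 80 | 30/110 = 27% | met (80 < 90) | not met (80 > 77) |
| 150 | 105 | 100 | 50/150 = 33% | met (100 < 105) | not met (100 > 90) |

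The readings can therefore disagree on either side of 128.6 mmHg. A third possibility is that the closing phrase refers to the choice of baseline measurement. The text does not settle it.

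**The case against.** The strongest reply is that the class is already fixed. The hypersensitivity definition applies to an illness "but does not meet the definition of anaphylaxis described above", Section 12.1.3.3 makes the criteria the means of diagnosis, and Table 4 is guidance on management. Its row also says that reactions may include the features, so urticaria alone or shortness of breath alone can sit there without conflict. This stands as far as it goes: a careful reader will arrive at anaphylaxis. But the row does not exclude the combination, and that reader is then left without a row.

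A reader might infer more than the documents support:

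- **Two ways of handling the product.** The criteria prescribe no treatment. The moderate hypersensitivity and severe rows handle the product in substance alike (stop, do not resume, discontinue), and final treatment is left to the investigator.
- **Epinephrine withheld through the wrong row.** The severe row lists "Epinephrine for bronchospasm, hypotension unresponsive to IV fluids, or angioedema". Urticaria with shortness of breath, without wheeze, names none of these.
- **Sites classifying differently.** The study has one center. Any inconsistency would be between assessors or occasions.
- **A distorted decision to open Cohort 3.** That step rests on the investigator's judgment of Cohort 1, which receives subcutaneous injections, whereas the row and the hypersensitivity definition are written for infusions. The reaction would be before the investigator under either label.
- **A clash between Table 4's mmHg grades and criterion 3.** One grades severity and the other supports a diagnosis, so they need not match.

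The reporting effect is also bounded. An event meeting a seriousness criterion is notified within 24 hours under either label (Section 12.4), and all adverse events are listed.

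**Conclusion.** The point holds as a contradiction within one appendix. Urticaria with shortness of breath meets the definition of anaphylaxis, is described by a row reserved for reactions that do not meet it, and has no other row. Criterion 3 is ambiguous as a separate matter, and the two readings give different answers for plausible pressures such as 110 falling to 80 mmHg.

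The consequence is limited to events that are not otherwise serious. For these, the label decides 24-hour AESI reporting and entry in the AESI table, where one event is 16.7 percentage points of a 6-subject active arm. This assumes that an assessor may classify from Table 4 rather than from the criteria. No effect on the pharmacokinetic results follows. The correction is worth making because it bears on recognising anaphylaxis and costs little.

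**What to change.** Amend Appendix 15.5 as follows:

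1. Reconcile the description of moderate hypersensitivity in Table 4 with the anaphylaxis criteria.
2. State in Table 4 that the Appendix 15.5 criteria take precedence for classification and AESI reporting, which the hypersensitivity definition already implies.
3. Identify which row of Table 4 applies to an event that meets the criteria.
4. Reconcile the 'or' in criterion 3 with its closing phrase, so that one limit results for any baseline.

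Which signs belong in which row, and which blood pressure limit is intended, is for the sponsor's safety physician; no clinical rule is proposed here. The cost is a wording change to one appendix, with no added assessment, sample or visit.
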